Hypothesis 2. ENDS participants will exhibit better asthma control and improved pulmonary function on measures of spirometry (i.e., PEF, FEV1, FVC, FEV1/FVC ratio, FEF25-75) and self-reported respiratory symptoms (wheezing, bronchitis, shortness of breath, mucus production, and other symptoms).

[figure not shown]
Secondary Aims

Aim 2a. Examine the effects of ENDS provision on inflammatory and disease biomarkers, including (IL-6, TNF- α , CXCL9, MMP9, FENO) and tobacco toxicant exposure (cotinine, CO, NNAL) at weeks baseline and week 8.

Hypothesis 4. Levels of both inflammatory biomarkers and tobacco toxicant exposure will be improved among participants randomized to ENDS relative to assessment-only control.

Aim 2b. Examine the effect of ENDS provision on intention to quit smoking and smoking cessation self-efficacy.

Hypothesis 5. ENDS participants will have higher quit intentions, and smoking cessation self-efficacy than controls.

3. Materials, Methods and Analysis. *The study design, methods and procedures must be adequately described in order for the IRB to understand all activities in which human subjects will participate. The IRB must also be able to differentiate those procedures that are performed for research purposes from those that are performed for routine care or evaluation.*

Design Overview: This study will use a between-subjects (N=30) randomized (unequally allocated 2:1), controlled design to investigating the influence of complimentary ENDS provision on combustible cigarette and ENDS use (including substitution of smoking for ENDS use), cigarette dependence, pulmonary function, and clinical indicators and biomarkers over 16 weeks. Eligible participants will be randomized to one of two conditions: 1) receive ENDS and e-liquid for 8 weeks, including encouragement to fully switch from cigarettes to ENDS; or, 2) an assessment-only control condition wherein participants may continue their usual cigarette smoking behaviors. The study involves initial and in-person screening, a baseline session and 8 weekly visits, and a 16-week follow-up visit (i.e., 8 weeks after discontinuation of complimentary ENDS provision to the experimental group).

ENDS selection: We intended to use JUUL for the ENDS condition due to its market share and nicotine delivery comparable to combustible cigarettes. However, due to shifting perceptions of JUUL related to EVALI and because the products have similar nicotine delivery profiles, we chose the VUSE Alto.

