Initial Screening: Potential participants will be recruited from the community, through referral from established community partnerships with immunology clinics facilitated by co-investigator and project mentor [name], and through recruitment and advertising partner BuildClinical (see section 5 for complete recruitment information). Computer-assisted screening will determine initial eligibility. Initial screening will query age, self-reported asthma history and symptoms, current smoking and ENDS use pattern, and intentions to quit smoking or engagement in behavioral or pharmacological smoking cessation. For adults meeting initial eligibility criteria, a research assistant (RA) will explain the purpose and procedures, provide information on confidentiality, answer questions, and schedule in-person screening, baseline assessment and randomization at Brown University's School of Public Health. All initial screening data will be destroyed once initial eligibility is determined.

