Baseline Visit (In-person Screening, Consent, and Randomization): Informed consent for in-person screening will be obtained. During the in-person screening, the CADRE CLC nurse practitioner will evaluate medical history to determine eligibility. In-person screening will include psychiatric screening, urine pregnancy test (for women), urine drug screen, breath alcohol via breathalyzer, and exhaled carbon monoxide via Bedfont Micro Smokerlyzer. Participants who arrive at the study intoxicated will be asked to stay at the study location until their Breath Alcohol (BrAC) reaches 0.04%, at which point they will be provided with transportation home by the study team. Participants will complete a medical screening questionnaire assessing their asthma and other medical history; the CLC nurse practitioner (NP) will evaluate medical eligibility and contraindications to nicotine use. Participants meeting all study criteria will complete informed consent (see section 5) and be enrolled in the study. Any participant reporting a course of oral steroids over the prior month will be rescheduled to a later date. Participants may also choose to be scheduled at a later date. Participants will be asked to withhold any short-acting β 2-agonists (SABA) for 8 hours prior to testing; if significant symptoms requiring SABA use occur, the assessment will be rescheduled. Measures will be completed per the schedule of measures below (see Table 1), including: demographic measures; measures of tobacco use, use history, and dependence; pulmonary function and asthma quality of life, symptomatology, and control; measures of mood; measures of cannabis use; and clinical biomarkers. Additionally, shared CLC measures will be administrated as described below. Following completion of baseline measures, participants will be randomized to complimentary ENDS condition or assessment-only control. Following completion of all scheduled measures and randomization, participants in the experimental condition will meet with aCAAS research staff unaffiliated with the project and will be allowed to experiment with available VUSE flavors. Participants will then be

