Primary purpose of visit	- Screening, randomization, and baseline	- Weekly assessments	- Weekly assessments - Clinical indicators and biomarkers	- Follow-up
Shared and Demographic Measures				
CLC Measures (see above)	X			
Screening (Eligibility) and Participant Safety Specific Measures				
Mini International Neuropsychiatric Interview (MINI 7.0.2)	X			
Breath alcohol (screening and participant safety)	X	X	X	X
Health Changes Questionnaire (participant safety ONLY)		X	X	X
Smoking Stages of Change Questionnaire	X			
Tobacco Use/Dependence Measures				
Combustible and ENDS Timeline Follow-Back (TLFB)	X	X	X	X
Minnesota Nicotine Withdrawal Scale (MNWS)	X	X	X	X
Brief Questionnaire on Smoking Urges (B-QSU)	X	X	X	X
Cigarette Use History (PATH Adapted)	X			
Fagerström Test for Cigarette Dependence (FTCD)	X		X	X
Penn State Dependence Index (PS)	X		X	X
Wisc. Inventory for Smoking Dep. Motives-Brief (WISDM)	X		X	X
Smoking Cessation Self-Efficacy Scale	X		X	X
Perceived Health Risk Scale	X		X	X
Respiratory Function Measures				
Pulmonary Function Test (PFT) via Spirometry	X		X	X
- Forced Expiratory Volume (FEV ₁)				
- Forced Vital Capacity (FVC)				
- Forced Expiratory Flow 25%-75% (FEF ₂₅₋₇₅)				
- Peak Expiratory Flow (PEF)				
Mini-Asthma Quality of Life Questionnaire	X	X	X	X
Asthma Symptoms Utility Index (ASUI)	X		X	X
Asthma Control Test (ACT)	X		X	X
Biomarkers (blood and breath)				
Carbon monoxide (CO)	X		X	X
Exhaled Nitric Oxide (FENO)	X		X	X
4-(Methylnitrosamino)-1-(3-pyridyl)-1-butanol (NNAL)	X		X	
Cotinine	X		X	
Interleukin-6 (IL-6)	X		X	
Tumor necrosis factor α (TNF- α)	X		X	
Matrix Metallopeptidase 9 (MMP-9)	X		X	
Chemokine ligand 9 (CXCL-9)	X		X	
Mood Measures				
Patient Health Questionnaire 9 (PHQ-9)	X		X	X
Generalized Anxiety Disorder 7 (GAD-7)	X		X	X
Cannabis Use/Dependence Measures				
Cannabis Use Disorders Identification Test-Revised (CUDIT-R)	X			

Weeks 1-8, 16: Participants who choose transportation to CAAS but arrive at the study intoxicated will be asked to stay at the study location until their Breath Alcohol (BrAC) reaches 0.04%, at which point they will be provided with transportation home by the study team. Participants will

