Thirty individuals age 21-65 with asthma and without other causes of airway obstruction such as COPD who are current combustible tobacco smokers and are not intending or planning to quit smoking will be screened and randomized. The rationale for including individuals with asthma who are not intending or planning to quit is that the risk for worsening respiratory symptoms is high with continued smoking, individuals are not otherwise engaged in behaviors such as smoking cessation which could reduce harm, and age 21-65 is a unique risk period for asthma exacerbation. By providing some eligible individuals in the experiment with ENDS and measuring pulmonary function, symptomatology, and biomarkers, we will expose these individuals to a level of risk that is either comparable or less (i.e., harm reduction associated with reduced smoking following complimentary ENDS provision) than that encountered in their day-to-day lives.

Inclusion Criteria

- a) Male or female (50%), 21 to 65 (inclusive) years of age;
- b) Persistent or intermittent asthma symptoms (i.e., episodic symptoms of airflow obstruction / airway hyperresponsiveness (AHR) as documented in CLC review of medical history);
- c) Currently prescribed SABA medication;
- d) Past-year smoking of ≥ 5 cigarettes/day;
- e) Exhaled CO ≥ 6 ppm at baseline;
- f) Zero breath alcohol during informed consent for participation;
- g) English-speaking at an 8th grade level.

Exclusion Criteria

- a) Intention to quit smoking during the next 30 days;
- b) Current engagement in any smoking cessation treatment;
- c) Current self-identification as regular ENDS user or using ENDS > 2 days / week;

- d) Medical contraindication to nicotine;
- e) Pregnancy (due to toxicity of nicotine and tobacco products);
- f) Urine-screened or past-month self-reported use of illicit substances (amphetamine, cocaine, methamphetamine, opioids, benzodiazepines);
- g) Current psychosis, mania, or suicidal ideation;

Note: Cannabis use will be assessed but not excluded.

Participants will need to speak English and be able to understand informed consent and questionnaires in English, which will be written at an 8th grade level.

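### Protocol Hypothesis 5 compares quit intention between arms, but no quit-intention measure is scheduled after randomisation

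*Protocol*

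**What the plan says.** Protocol Part III, section 2, lists Aim 2b among the secondary aims. Its hypothesis is a comparison of the two arms on two separate constructs: "ENDS participants will have higher quit intentions, and smoking cessation self-efficacy than controls".

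Table 1 (Part III, section 3) has one row that bears on readiness or intention to quit, the "Smoking Stages of Change Questionnaire". It stands under "Screening (Eligibility) and Participant Safety Specific Measures" and is marked at Baseline only. The other construct is covered by the "Smoking Cessation Self-Efficacy Scale", marked at Baseline, Week 8 and Week 16.

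On timing, the Baseline Visit paragraph states: "Following completion of baseline measures, participants will be randomized to complimentary ENDS condition or assessment-only control". Quit intention is also asked at initial screening, of which the protocol says: "All initial screening data will be destroyed once initial eligibility is determined". Exclusion criterion (a) in section 4 is "Intention to quit smoking during the next 30 days".

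The SAP names neither quit intention nor self-efficacy as a dependent variable. Its own Hypothesis 5 carries the same number but concerns acceptability.

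**The concern.** A claim that one randomised arm ends with higher quit intention than the other needs quit intention recorded after randomisation in both arms. The schedule appears to record it only beforehand, as part of deciding who may enter. If so, a stated secondary question has no outcome data, and the loss is permanent for each participant once the Week 8 and Week 16 visits have passed.

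This matters more than low power does. The documents accept that the trial is too small to detect group differences and justify it as a pilot that will indicate the size of effects for later studies. An imprecise estimate serves that purpose; no estimate does not.

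**Working it through.** The plan gives no figure for this point, so the check is a trace of each construct through the documents, followed by a count.

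**1. What the hypothesis needs.** For a visit t after randomisation (Week 8 or Week 16), the quantity is: summary of outcome at t in the ENDS arm minus summary of outcome at t in the control arm. Both terms require data at t.

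**2. What Table 1 schedules.**

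| Row | Block | Baseline | Weeks 1–7 | Week 8 | Week 16 |
|---|---|---|---|---|---|
| Smoking Stages of Change Questionnaire | Screening and safety | X | – | – | – |
| Health Changes Questionnaire | Screening and safety | – | X | X | X |
| Smoking Cessation Self-Efficacy Scale | Tobacco use | X | – | X | X |
| Timeline follow-back (TLFB) | Tobacco use | X | X | X | X |

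The single mark is unlikely to come from a broken table. The Health Changes row in the same block keeps its blank at Baseline and its three later marks, and the self-efficacy row keeps its own pattern.

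**3. Whether another passage fills the gap.**
- *Visit narrative (Weeks 1-8, 16).* The extra Week 8 and 16 measures it lists include self-efficacy but not quit intention. The list is not complete (it omits the Perceived Health Risk Scale, which Table 1 marks at both visits), so its silence supports the reading of Table 1 but would not settle the matter alone.
- *Initial screening.* Quit intention is asked, but before randomisation, and the answers are destroyed.
- *Shared CLC battery.* No quit-intention measure is listed, and the battery is given at Baseline only.
- *SAP, Quantitative Analyses.* Neither Aim 2b outcome is a dependent variable: 0 of 2.

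**4. Whether the Baseline value can stand in.** It cannot. It is taken before allocation, so a difference between arms at that point reflects chance and not ENDS provision. It also comes from a sample from which people intending to quit within 30 days have been excluded.

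**5. Whether another outcome can stand in.** The TLFB records behaviour, the dependence scales record dependence, and the self-efficacy scale records confidence. The hypothesis itself names intention and self-efficacy separately. The Health Changes row is reserved for participant safety.

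**6. Count.**
- Possible assessments at Weeks 8 and 16: 30 × 2 = 60. After the planned 10% dropout: 30 × 0.9 = 27, and 27 × 2 = 54.
- Scheduled for quit intention: 0 of 60 (0 of 54 after dropout).
- Scheduled for self-efficacy: 60 of 60.

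**The case against.** The strongest case on the other side has three parts.

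*The instrument is inferred.* No passage names the Stages of Change Questionnaire as the Aim 2b outcome; Table 1 files it as an eligibility measure. A reader might infer that the designated outcome instrument was put in the wrong columns. The documents do not support that, because no outcome instrument is designated. This stands, and the claim is therefore limited to the absence of any named measure after randomisation. The gap does not depend on the inference: if another instrument was intended, it is not scheduled either.

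*The questionnaires were not seen.* Part IX says that data collection materials are attached to the application, and they are not in the public documents. An intention item inside one of the Week 8 or Week 16 questionnaires cannot be ruled out. A reader might infer that the trial certainly collects nothing on quit intention after Baseline; the documents show only that nothing is named. This caveat stands. It does not show that such an item exists, and an outcome found only inside another form would still need to be identified in the plan.

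*The consequence is small.* This is half of one secondary hypothesis in a pilot of 30. Smoking behaviour is recorded at every visit, and the SAP will compare smoking reduction and cessation across arms. All of this is correct and limits the weight of the point. It does not answer it, because behaviour is a different outcome from intention.

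**Conclusion.** The point holds as an inconsistency between a stated aim and the schedule. As written, the plan provides no post-randomisation data with which to estimate the quit-intention half of Protocol Hypothesis 5, even descriptively. The size is 0 of 60 scheduled assessments, against 60 of 60 for self-efficacy.

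This rests on Table 1, the visit narrative and the SAP being the complete account of what is measured, subject to the unseen attachments. It should be fixed, but it is not a threat to the trial.

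A reader might go further and infer that Aim 2b as a whole fails, or that the primary aims are weakened. The documents do not support either. Self-efficacy is measured at Baseline, Week 8 and Week 16 and lacks only a named analysis in the SAP. The tobacco-use and respiratory outcomes do not depend on quit intention. Nor do the documents allow a numerical effect or bias to be attached to the gap, since they give no rates of quit intention in either arm.

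**What to change.** 1. **Measure it or remove it.** Either add the Smoking Stages of Change Questionnaire, or another quit-intention measure, to the Week 8 and Week 16 columns of Table 1 and name it as the Aim 2b measure, or delete quit intention from Aim 2b and Hypothesis 5.

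2. **If it is measured, state the scoring in advance,** including how participants who have already stopped smoking are classified. They should stay in the randomised denominator, because dropping them would condition the comparison on something that the intervention may change. One workable way is to identify them from the TLFB, already collected at both visits, and to show them as a separate category in each arm.

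3. **Align the SAP.** List self-efficacy, and quit intention if measured, as secondary dependent variables for Aim 2b. Report the ENDS-versus-control estimate with its 95% confidence interval at Weeks 8 and 16, labelled as descriptive.

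4. **Treat separately** the SAP's hypotheses on acceptability and barriers. The exit interviews they rely on appear in neither Table 1 nor the visit text: schedule the interview or delete the hypothesis. No Aim 2b data depend on this.

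The cost of measuring is a few minutes of a questionnaire already in the study at two existing visits (about 1 hour at Week 8 and 20 minutes at Week 16, by the compensation section), a short SAP addition and a minor amendment. Deletion costs only a text change but gives up the question. The between-arm estimates will stay imprecise in either case, as the documents already acknowledge for group differences.

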DOCUMENT: Statistical Design and Power

PROTOCOL TITLE: Complimentary Electronic Cigarettes for Harm Reduction among Adult Smokers with Asthma

NCT: NCT05278065

DOCUMENT DATE: 06/17/2020

Statistical Design and Power

Statistical Design

Initial data analysis will include descriptive analysis for the sample and within study condition, tests of attrition, missing data analysis, evaluation of distributional properties, and correlations among measures. Potential moderators of treatment outcome (e.g., compliance) will also be examined.

Quantitative Analyses

Aim 1 - Hypothesis 1: At Week 8, ENDS participants will smoke fewer cigarettes/day (CPD) and show reduced cigarette dependence relative to BL. Relative rates of CPD reduction and cessation across study arms will be examined. DVs: cigarettes per day (from TLFB); FTCD and WISDM scores. IVs: time; condition; time by condition interaction.

Aim 2 - Hypothesis 2: ENDS participants will exhibit better asthma control and self-reported respiratory symptoms (wheezing, bronchitis, shortness of breath, mucus production) versus baseline. Changes in lung function will be explored. Primary DVs: Asthma Control: ACT scores, Asthma Symptoms: ASUI scores, Mini-AQLQ scores; Secondary DVs: Spirometry: PEF, FEV₁, FVC, FEV₁/FVC ratio, and FEF₂₅₋₇₅. IVs: time; condition; time by condition interaction.

Aim 3 - Hypothesis 3: Biomarkers of exposure, toxicity, and inflammation will be lower in ENDS participants versus BL. DVs: Inflammatory and Disease Biomarkers: IL-6, FENO, Exposure and Toxicity: NNAL, TNE, TNE/NNAL ratio. IVs: time; condition; time by condition interaction.

Qualitative Analyses

Aim 4 - Hypothesis 4: High willingness to participate, high weekly retention, low attrition, and few reported barriers to engagement will demonstrate feasibility of complimentary ENDS provision for cigarette substitution. Hypothesis 5: Positive responses during qualitative exit interviews will demonstrate acceptability.

Analytic approach:

Multiple approaches will be used to investigate smoking/ENDS use; respiratory function; and inflammatory and disease marker outcomes but will primarily focus on developing a longitudinal model based on intent-to-treat principles. Initially, t-tests (paired and independent samples) will quantify differences in outcomes across groups or time, and ANOVA will be used to investigate within, between, and within-between interactions. We will leverage the robustness of linear mixed effects models (LMEM) or generalized estimating equations (GEE) to examine outcomes within a longitudinal framework. Intraclass correlations (ICCs) of outcome variables within participant classes will be investigated. Model terms will include time, condition, and their interaction, and covary for potentially unbalanced baseline demographic and behavioral (e.g., smoking) factors across conditions. LMEM models will include random intercepts to account for subject-level differences in outcomes and investigate fixed linear, quadratic, and subject-level random effects of time. Appropriate LMEMs will be selected based on the distributional properties of the DV. We will investigate logarithmic transformations of the outcome where necessary. DVs with high resolution data (e.g., measure of cigarettes per day available weekly), will be modeled at the weekly level. All analyses will be conducted in R version 3.6.0, using the geepack package for GEE and lme4 package for LMEMs.

Missing data:

Systematic missing data due to attrition or other factors will be examined. We will first conduct Little's MCAR test on a dataset including all participant characteristics, covariates, primary, and secondary outcomes to evaluate whether missing data patterns are consistent with the Missing Completely at Random (MCAR) assumption. As data in longitudinal studies is rarely MCAR, we will initially use the VIM package in R to identify patterns of systematic missingness across time. We will also use t-tests and χ^2 tests to examine whether covariates and outcomes at week 8 vary as a factor of attrition at subsequent time points. Multiple-imputation will be used for sensitivity analyses of all primary and secondary outcome models following identification of predictors of missingness to help sustain the missing-at-random (MAR) assumption. Multiple imputation will be conducted in the *mice* package for R.

Power Analysis and Sample Size

Tobacco use outcomes: Power and sample size calculations were conducted in GPower 3.1 based on between- and within-subjects analyses. [name] pilot trial examining 6 weeks of complimentary ENDS provision on tobacco use behaviors and nicotine dependence at weeks 6 and 10 (i.e., 4 weeks after final ENDS provision) found significant reductions between baseline and both time points in average cigarettes per day (baseline=19.6(8.2); week 6=6.7(7.9), $d=1.64$; week 10=8.8(8.3), $d=1.12$) and cigarette dependence (baseline=5.94(1.96); week 6=3.89(2.78), $d=.88$; week 10=3.50(3.08), $d=1.03$); all with large effects. However, given the unknown effect of providing free ENDS to adult smokers with asthma and the limited interpretability of effect sizes from pilot trials we chose to use a more conservative medium-large ($d=0.65$) effect size. With our planned enrollment ($N=30$), anticipated 10% dropout, and target power ($1-\beta=.8$), sample size was adequate to detect within-subject repeated measures (Aim 1) differences in the intervention (ENDS) group but was inadequate to detect between-subjects effects (i.e., group differences). Although power is below .80 to detect group differences, this pilot proposal will help determine the magnitude of these effects and inform the design of future research.

Respiratory outcomes: Investigations of respiratory symptoms and lung function change in 'healthy' smokers switching to ENDS have found very large ($h=1.94$) within-subjects effects for cough, very large ($h=1.50$) within-subjects effects for shortness of breath, and large ($d=.998$) within-subjects effects for FEF₂₅₋₇₅; also found were large ($d=.921$) between-subjects effects comparing successful to failed switchers. As these improvements may be even more pronounced for adults with asthma, the current planned enrollment achieves adequate power to examine these within-subjects (but not between-subjects) outcomes within the ENDS condition per the power and sample size analyses outlined above (Aim 3). However, analysis of spirometry are limited by the short follow-up period for the proposed pilot within-which changes in these metrics are not anticipated. As with the tobacco use outcomes, although power is below .80 to detect group differences, this pilot proposal will help determine the magnitude of these effects and inform the design of future research.

Biomarker: The effect of complimentary ENDS provision on biomarkers of exposure, toxicity, and inflammation in adults with asthma in real-world use conditions should be considered exploratory and preparatory for future intervention design.

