provided with a complimentary VUSE device and VUSE pods consistent with their preferred flavor. Participants will be provided with a number of VUSE pods comparable to 150% of their weekly consumption of nicotine based on their responses to the baseline timeline follow-back (TLFB). This quantity will ensure that participants have adequate VUSE pods to fully substitute combustible cigarettes within a reasonable margin of error (e.g., timing/ scheduling of the next session), should they choose to do so. As each standard VUSE pod provides an amount of nicotine comparable to one pack of cigarettes (i.e., 20 cigarettes), we will compute participants' average weekly cigarette consumption in packs and provide 1.5x that number of VUSE pods rounded up to the nearest two pods (VUSE Alto pods are packaged in sets of 2 pods). VUSE recipients will either return to lab each week with all used and unused VUSE pods or CAAS research staff will meet participants at their home to collect unused pods as a secondary verification of self-reported ENDS use behavior.

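### The SAP names compliance, a post-randomisation variable, as its example of a treatment moderator, a role in which it cannot show effect modification

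*SAP*

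**What the plan says.** The SAP's Statistical Design section opens with a paragraph on preliminary work: "Initial data analysis will include descriptive analysis for the sample and within study condition", followed by attrition tests, missing-data analysis, distributional checks and correlations. That paragraph ends: "Potential moderators of treatment outcome (e.g., compliance) will also be examined". Nothing else in the SAP deals with moderation. Neither document defines compliance, gives its arm or time window, names a model for it, or sets out a method for a variable that arises after randomisation.

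The Protocol's Design Overview (Part III, section 3) describes the two arms. One will "receive ENDS and e-liquid for 8 weeks, including encouragement to fully switch from cigarettes to ENDS". The other is "an assessment-only control condition wherein participants may continue their usual cigarette smoking behaviors".

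Under Baseline Visit, the Protocol adds a product check for one arm only: "VUSE recipients will either return to lab each week with all used and unused VUSE pods", or staff collect pods at the participant's home. The stated purpose is "as a secondary verification of self-reported ENDS use behavior". The self-report being verified is the combustible and ENDS Timeline Follow-Back (TLFB). Table 1 schedules it at baseline, Weeks 1-7, Week 8 and Week 16, with no restriction by arm.

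The main analysis (SAP, Analytic approach) "will primarily focus on developing a longitudinal model based on intent-to-treat principles". Its terms are time, condition, their interaction and baseline covariates. Compliance is not among them, nor is it listed as an independent variable for any aim.

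**The concern.** A moderator analysis asks whether the effect of assignment differs between kinds of participant. The variable that defines those kinds must be fixed before assignment and must exist in both arms, so that each level contains a randomised comparison. Compliance with the assigned product meets neither condition.

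Without that comparison, the natural analysis sets better compliers against worse compliers within the ENDS arm. People who use the product faithfully may differ in motivation, dependence or baseline smoking, and may have done better without it. For cigarettes per day the problem is close to circular: participants are encouraged to switch fully, so one who does so smokes fewer cigarettes almost by definition.

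What is at stake is interpretation. The SAP concedes inadequate between-group power, states Hypotheses 1 to 3 against baseline for ENDS participants, and says the pilot should inform later research. A contrast between compliers, reported under the label of moderation, could be read as evidence about who benefits from ENDS.

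**Working it through.** The SAP attaches no figure to compliance, so most of this check is reasoning, with arithmetic for scale.

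**1. Numbers available.** N = 30 at 2:1 gives 20 ENDS and 10 control. With 10% dropout, 20 × 0.9 = 18 and 10 × 0.9 = 9.

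**2. The plan's nearest figure.** The SAP says between-group power is below .80 at d = 0.65. For 18 versus 9, the noncentrality is 0.65 / √(1/18 + 1/9) = 0.65 / 0.408 = 1.59 on 25 df. Two-sided power is 0.334, with alpha 0.05 assumed because none is stated. The concession is confirmed. The point about compliance does not depend on it.

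**3. Possible meanings of compliance.**

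| Meaning | In control arm? | Fixed before randomisation? | Condition-by-compliance term |
|---|---|---|---|
| Use of assigned ENDS (pods) | No | No | Cannot be estimated |
| ENDS days on TLFB | Recorded, but not use of an assigned product | No | Can be fitted; not effect modification |
| Attendance at visits and assessments | Yes | No | Can be fitted; not effect modification |

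For the first row, write Y = b0 + b1·Z + b2·C + b3·Z·C, with Z = 1 for ENDS and C for compliance. If C is undefined when Z = 0, the control arm says nothing about b2. If C is set to 0 for controls, then C and Z·C are the same column, and b2 and b3 cannot be separated. Only the slope of Y on C within the ENDS arm remains, and C was not randomised.

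**4. A link to baseline smoking in the design itself.** Under Baseline Visit, weekly pod supply is 1.5 times baseline packs per week, rounded up to an even number. At the entry minimum of 5 cigarettes/day this is 5 × 7 / 20 = 1.75 packs, × 1.5 = 2.63, so 4 pods. At 19.6/day (the baseline mean of the pilot trial cited in the SAP) it is 6.86 packs, × 1.5 = 10.29, so 12 pods. A raw count of pods used therefore has a ceiling that rises with baseline smoking.

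**5. Possible size (illustration).** Assume no ENDS effect, no moderation, and compliance correlated r with outcome through prognosis alone. For bivariate normal variables, the halves of a median split differ by 2 × r × 0.798 SD.

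- r = 0.3: 2 × 0.3 × 0.798 = 0.48 SD
- r = 0.4: 2 × 0.4 × 0.798 = 0.64 SD
- r = 0.5: 2 × 0.5 × 0.798 = 0.80 SD

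A simulation at n = 18 (20,000 runs) gives slightly smaller differences, because half-sample means are less extreme in small samples:

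| r | Split difference (SD) | Two-sided 5% test of the compliance-outcome correlation significant |
|---|---|---|
| 0 | about 0 | 4.9% |
| 0.3 | 0.45 | 22.7% |
| 0.5 | 0.76 | 59.0% |

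The documents give no value for r and do not specify a split.

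**6. Precision of a valid alternative.** In SD units, the main between-group contrast at 20 versus 10 has standard error √(1/20 + 1/10) = 0.387. For a baseline factor that halves each arm, the interaction has √(1/10 + 1/10 + 1/5 + 1/5) = 0.775, twice as large.

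**The case against.** The strongest reply is that the SAP commits to very little. The sentence is one exploratory item among data checks. It specifies no interaction term, no split and no effect claim, so confounding is a likely consequence of acting on it rather than something the plan is shown to do. That stands, and it limits the severity.

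Three stronger readings are tempting, and the documents do not support them.

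- *Compliance exists only in the ENDS arm.* This is true of compliance with the assigned product. But the word is undefined, visits apply to both arms, and the ENDS TLFB has no arm restriction. Controls are not barred from ENDS, and the exclusion criteria admit use on up to 2 days a week. The claim must stay conditional on the definition.
- *The trial's analysis is confounded.* The intent-to-treat models contain no compliance term, so no planned primary or secondary estimate is affected.
- *The spurious difference rivals the design effect of 0.65.* The SAP claims adequate power at d = 0.65 only for within-subject change in the ENDS group. The figures in step 5 are between-person differences in outcome. They are standardised differently and should not be compared.

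It is also fair to say that harm to a later trial is speculative: the SAP itself doubts pilot effect sizes, and nothing says compliance results will be used for sizing. None of this turns a post-randomisation variable into a valid moderator.

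**Conclusion.** The point holds in a limited form. The SAP's only named moderator arises after randomisation under every plausible definition, so analysing it cannot show effect modification. If it means use of the assigned ENDS, the interaction cannot be estimated and the remaining comparison, among about 18 to 20 people, cannot separate adherence from prognosis. This conclusion is structural and needs no numerical assumption.

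The size does need assumptions. The range of roughly 0.45 to 0.8 SD rests on a purely prognostic correlation of 0.3 to 0.5, normality and a median split, none of which comes from the documents. It shows that a sizeable artefact is possible, not that one is expected.

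Severity is low to moderate, because the defect is confined to one exploratory statement.

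**What to change.** Amend the sentence in the SAP's Statistical Design section as follows.

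1. Delete compliance as the example of a moderator.
2. Restrict condition-by-variable analyses to baseline measures already in Table 1, such as TLFB cigarettes/day, FTCD and ACT. Label them exploratory, given about 20 versus 10 participants. Prior ENDS use is a weaker candidate because the exclusion criteria truncate its range.
3. Define compliance with ENDS (for example pods used and TLFB ENDS days, with a time window). Report it descriptively within the ENDS arm, with no claim about treatment effect or effect modification. If pods are counted, show them relative to pods supplied, because supply depends on baseline smoking.

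If the team does want a causal statement about adherence, it needs a pre-specified estimand and its assumptions in place of a moderator label.

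The cost is SAP wording only: no new data, visits or participants. The downsides are that compliance results can no longer be presented as effect modification, and that the baseline interactions will be imprecise, with about twice the standard error of an already underpowered group comparison.
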